8. *Objectives*

The objective of this research study is to better understand patterns of recovery after total hip arthroplasty (THA) and total knee arthroplasty (TKA). The study will evaluate how pain, pupil diameter as a measure of LC activity and cognitive (i.e., thinking style) determine patterns of recovery, and the study will evaluate the efficacy of gabapentin versus placebo for improving recovery after surgery.

Research hypothesis: The null hypothesis (H_0) is that modeled trajectory of change in pain intensity report after THA and TKA does not differ between oral gabapentin and placebo in a manner dependent on its interaction with preferred cognitive style and pre-surgery pupil resting diameter. The alternative hypothesis (H_1) is that there is a difference between the two groups which is dependent on these interactions. The null hypothesis will be tested through contrasting the fit of a null model (m_0), with only change parameters and prognostic covariates, and the full model (m_1), which includes all of the predictors in null model with the addition of randomized treatment group, cognitive style, resting pupil diameter, and all two and three-way interactions. The difference in fit will be evaluated using a likelihood ratio test, as further described below.

$$H_0: -2 * (\loglik[m_0] - \loglik[m_1]) = 0$$

$$H_1: -2 * (\loglik[m_0] - \loglik[m_1]) > 0$$

Study objective: The primary objective is to determine the effectiveness of oral gabapentin to speed recovery from pain, as measured by growth curve modeling, after THA or TKA and how this effectiveness is modified by preferred cognitive style and pre-surgery resting pupil diameter.

Secondary objectives are planned to explore the role of these factors interact to predict other outcomes from surgery, including speed of gain in activity, assessed by actigraphy, speed recovery from self-assessed disability, and time to cessation of opioid use; to explore whether change in pupil diameter to acute experimental pain explains additional variance in a 4-way interaction compared to the 3-way interaction in the primary analysis.

Section 3: Trial Methods

9. Trial design

[figure not shown]
The trial is a two-center, randomized, double-blinded, parallel-group, placebo-controlled trial. Treatment allocation is a 1:1 ratio. Patients are randomized to either gabapentin or placebo control.

10. Randomization

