A computer-generated randomization using a 1:1 allocation ratio in permuted blocks of 8 will be developed by the study statistician uninvolved with data collection and administered by the research pharmacist at Wake Forest School of Medicine. The 'blockrand' package in R will be used by the study statistician. The randomization will be stratified based on study recruitment site, concurrent use of a serotonin-norepinephrine reuptake inhibitor, and chronic low- or high-dose opioid therapy. Allocation will be conducted by the research pharmacist and will occur after consent and completion of the first visit. At all times, the allocation assignment will be concealed from the study coordinator and other investigators who manage participant recruitment and follow-up. Allocation concealment is maintained using a centralized pharmacy administration of study drug. Both study agents are designed to look identical to each other to maintain blinding.

11. Sample size

To calculate the statistical power for our analytical strategies, we simulated scenarios for which we instilled known relationships between the random effects of change models as well as a range of predictors of those parameters that were themselves correlated. A sample size of 250 was to determine to provide substantial power (> 90%) to detect clinically significant differences between a null model versus a demographic/perioperative + psychosocial predictors model using a likelihood ratio test. An example of the expected differences is displayed (left) that illustrates a three-way interaction between treatment (Placebo vs Gabapentin), cognitive-affective style (Optimist vs Catastrophizing), and pupil size (Low, Mid, High).

12. Framework

Superiority testing will be used to examine difference between the effect of treatment alone on the change process in pain after surgery and the effect of treatment as interacting with preferred cognitive style and pre-surgery pupil responses to painful stimuli.

13a. Information on interim analyses

There are no planned interim analyses.

13b. Any planned adjustment of the significance level due to interim analysis

None.

13c. *Details of guidelines for stopping a trial early*

There is no plan to stop the trial early aside from recommendations based on unanticipated serious adverse events by the DSMB.

14. *Timing of final analysis*

Table 1. Timing of study measures

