Study period	Screen	Baseline	In hospital	Daily diaries	Follow up 1	Follow up 2	Phone	Orthopaedic clinic visits
Visit number	0	Visit 1			Visit 2	Visit 3		
Week		-4 to -2*	0-3 days	0-8	8	26	12,16,20,52	2, 6, 12-16, 26, 52
Informed consent		X						
Demographic		X						
Medical/surgical history		X						
Questionnaires		X			X	X		
Pain testing & pupillometry		X						
Randomisation		X						
Study drug dispensing		X						
In hospital pain/medication data & disposition			X					
Daily diary & accelerometry		X		X				
Phone assessment of pain, medication use, function							X	
Joint function								X

*Study medication begins at -2 weeks and continues until 3 weeks after surgery

Final analysis of the gabapentin vs placebo comparison with and without inclusion of interactions with preferred cognitive style and pre-surgery pupil responses to pain will take place when all patients have completed the 12-month follow-up and data for the primary endpoint have been cleaned, which occurred in May 2022. Results were anticipated to be posted by Jan, 2023, but complexities associated with generation of a novel psychologic construct from the final dataset and defining parameters for pupil assessment prevented completion of the primary analysis until Mar, 2023.

15. *Timing of outcome assessments*

The schedule of study procedures is provided in the protocol and summarized in the table below.

Section 4: Statistical Principles

16. *Level of statistical significance*

All applicable statistical tests will be 2-sided and will be performed using a 5% significance level.

17. *Adjusting for multiplicity*

The primary analysis involves a single model-based inference that will be interpreted at the 5% threshold of statistical significance. If the primary analysis is significant, each main factor, all two way interactions, and the three way interactions will be evaluated and each will be interpreted at the 5% level of significance with no adjustments made for multiplicity.

18. *Confidence intervals*

All confidence intervals presented will be 95% and two-sided.

19a. *Definition of adherence to the intervention and how it is assessed*

Compliance is assessed based on the number of daily diary entries after hospital discharge. It is defined as:

$$\% \text{ compliance} = (\text{number of entries}/\text{number of days entries were to be completed}) * 100\%$$

19b. *How adherence will be presented*

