The primary analysis will model trajectory of recovery of daily worst pain ratings and examine several sources of influence on this recovery. Sometimes referred to as mixed-effects models, or hierarchical linear models, growth curve modeling allows specification of a change trajectory that is unique to each individual. The nature of the common form of changes in daily pain will be modeled using a curvilinear form (e.g., polynomial regression). Through the use of fixed and random effects, variations in intercepts (i.e., levels of pain on day of discharge) and slopes (i.e., change in daily pain over time) can be examined using the pre-specified influences outlined below. To model individual pain trajectories, several model form candidates will be examined with the best fit determined using a Bayesian Information Criterion. These model forms will include linear, quadratic, cubic, and log(time), and each of these model candidates will be employed that reflect a fundamental change in trajectory that occurs during the observation period. Based on preliminary data it is highly likely that a log(time) form will be chosen.^{1,2}

To examine the proposed hypotheses, several key sets of predictors will be specified including patient characteristics, operative characteristics, cognitive style, randomized treatment assignment, and pre-operative pupil diameter response. Each of these predictors are described below:

Patient characteristics: To adjust the associations for individual age and sex will be entered into the model.

Operative characteristics: To adjust the associations for any subtle differences in medical care, study site, and surgery type (hip or knee arthroplasty) will be entered into the model.

Cognitive style: Multidimensional scaling of the pre-operative questionnaires will be conducted to create a unidimensional scale that represents a broader spectrum of cognitive style that ranges from optimism/acceptance of pain to catastrophizing. This novel predictor will be examined for reliability and correlations with the original scales. If insufficient reliability ($\alpha < 0.70$) or construct validity ($r < |0.40|$) with the original scales cannot be obtained, the analysis will proceed using the originally scaled catastrophizing predictor.

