Pupil diameter: Pupil recordings will be conditioned to remove artifacts (e.g., blinks), saccades, and deviations from central gaze that might bias recordings. A response window with appropriate lag reflecting delayed onset of pupil response due to physiological delays will be used to define change in diameter to each stimulus as previously reported.¹⁷ Two pupil measurements will be estimated from the session data, the mean pupil diameter during baseline (i.e., pre-stimulus) and the modeled response to pupil to 50-degree stimulus.

Gabapentin: Randomized treatment assignment of either gabapentin or placebo will be a fundamental predictor of trajectory.

These individual predictors sets will then be used to test the primary hypothesis that gabapentin alters time course of recovery after arthroplasty in a manner dependent on its interaction with preferred cognitive style and pre-surgery pupil diameter. The primary statistical inference will be the difference in the likelihood ratio between two nested models using a chi-square test with K degrees of freedom (i.e., K being the difference in the number of parameters between the two models). The first model (i.e., null model) will consist of the pain trajectory model with the addition of patient characteristics and operative characteristics. The second nested model will add medication assignment (gabapentin versus placebo), cognitive style (catastrophizing \leftrightarrow optimism latent score), and resting pupil diameter, and all two-way interactions and three-way interaction between these 3 predictors (i.e., 3 two-way, and 1 three-way interaction for both intercept and slope parameters) from the first nested model. This approach allows a single likelihood ratio test of the primary hypothesis and will be interpreted using a two-tailed hypothesis test using $p < 0.05$. A statistically significant difference in the likelihood ratio test will be interpreted as evidence to support the primary hypothesis in that the interaction of these predictors impacts some aspect of the change process beyond that of the basic model. We have planned several sensitivity analyses using multiple imputation to account for missing data.

Several exploratory secondary analyses of the data set:

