There is a large literature demonstrating a positive correlation between the extent of pain catastrophizing with pain, disability, and opioid use and a negative correlation with activity. Since the cognitive construct to be used in both the primary analysis and the secondary analyses is derived from the pain catastrophizing instrument, adjustment of modeled trajectories by preoperative pain, activity disability, and opioid use would be expected to diminish the independent effect of the cognitive construct in these analyses. The adjustments in modeling using these preoperative variables were intended as sensitivity analyses rather than testing the primary and secondary hypotheses. This mistake was identified and this amendment was prepared and submitted prior to performing analyses using these adjustments.

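### The primary likelihood ratio test bundles treatment, cognitive style, pupil diameter and all interactions, so a cognitive-style effect alone can be declared support for the gabapentin interaction hypothesis

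*SAP*

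**What the plan says.** Item 8 of the SAP words the null and alternative hypotheses as a gabapentin–placebo difference in trajectory that depends on interaction with cognitive style and resting pupil diameter. The study objective in the same item opens more broadly: "The primary objective is to determine the effectiveness of oral gabapentin to speed recovery from pain".

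The test is defined in item 8 and again in item 27a/27b. The null model contains the trajectory, age, sex, study site and surgery type. The full model is the null model "with the addition of randomized treatment group, cognitive style, resting pupil diameter, and all two and three-way interactions", acting on both intercept and slope. The two are compared by one likelihood ratio test at 5%. Item 27a/27b says that a significant result "will be interpreted as evidence to support the primary hypothesis in that the interaction of these predictors impacts some aspect of the change process".

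Three other places bear on this:

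- Item 12 describes another contrast: "Superiority testing will be used to examine difference between the effect of treatment alone on the change process in pain after surgery". The comparator there is treatment acting through its interactions with style and pupil.
- Item 17 says that, after a significant primary result, "each main factor, all two way interactions, and the three way interactions will be evaluated and each will be interpreted at the 5% level", without multiplicity adjustment.
- The Appendix, under SAP 2.2, states: "There is a large literature demonstrating a positive correlation between the extent of pain catastrophizing with pain, disability, and opioid use".

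**The concern.** Rejecting an omnibus test shows that at least one added term is non-zero. It does not show which one. Here the added terms include the main effects of style and pupil and their mutual interaction, none of which involves the randomised treatment. The SAP nevertheless reads any rejection as evidence about the interaction.

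The term most likely to be non-zero is the one the SAP already expects: an association between catastrophizing and pain. SAP 2.2 removed adjustment for baseline pain partly so that this association would not be diminished. The trial's one confirmatory p-value could therefore be significant when gabapentin has no effect and interacts with nothing, and the written rule would still count the hypothesis as supported.

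**Working it through.** **Degrees of freedom.** The full model adds 3 main effects + 3 two-way terms + 1 three-way term = 7 terms, each on every growth parameter. Item 27a/27b lists linear, quadratic, cubic and log(time) as candidate forms and expects log(time).

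| Form | Growth parameters | Full test | All treatment terms (4) | Treatment interactions (3) |
|---|---|---|---|---|
| linear or log(time) | 2 | 14 | 8 | 6 |
| quadratic | 3 | 21 | 12 | 9 |
| cubic | 4 | 28 | 16 | 12 |

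Of the 14: style, pupil and style × pupil take 3 × 2 = 6; the gabapentin main effect takes 2; gabapentin interactions take 6.

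**The plan's own figure.** Item 11 gives more than 90% power with 250 patients, from a simulation whose effect sizes and variances are not stated. It cannot be reproduced and is not called wrong. It is described as a comparison of a null model with a demographic/perioperative plus psychosocial predictors model, so it does not show power for a gabapentin interaction.

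**Analytic check.** Set every gabapentin, pupil and interaction term to zero. Let style correlate at r with the person-level intercept only. The SAP gives no r, so 0.1 to 0.4 is assumed. The noncentrality is λ = 245 r²/(1 − r²), where 245 is 250 less the constant and four covariates. If intercept and slope correlate at −0.4, divide λ by 1 − 0.16 = 0.84. The 5% critical value on 14 df is 23.68. Diary noise is ignored here.

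| r | λ (correlation 0) | λ (correlation −0.4) | Rejection, 14 df |
|---|---|---|---|
| 0.1 | 2.47 | 2.95 | 12–14% |
| 0.2 | 10.21 | 12.15 | 48–57% |
| 0.3 | 24.23 | 28.85 | 92–96% |
| 0.4 | 46.67 | 55.56 | about 100% |

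At r = 0.3, 21 df gives 86–93% and 28 df gives 81–89%, so the choice of trajectory form does not remove the problem.

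**Simulation with diary noise.** There were 4,000 trials per null scenario, with 250 patients and complete diaries on days 0–56 under log(day + 1). Assumed values: between-person SD 2.0 (intercept) and 0.6 (slope), residual SD 1.5 with AR(1) 0.4. The test was adjusted for age, sex, site and surgery type.

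| r | 14 df, correlation −0.4 | 14 df, correlation 0 | 8 df or 6 df |
|---|---|---|---|
| 0.1 | 16% | 13% | 6–7% |
| 0.2 | 55% | 42% | 6–7% |
| 0.3 | 94% | 84% | 6–7% |
| 0.4 | 100% | 99% | 6–7% |

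With r = 0 the three tests reject in 6.7%, 6.3% and 6.2%, so the chi-square reference is slightly liberal. A second simulation (5,000 trials per scenario) gave 36%, 62%, 85%, 96% and above 99% for the 14-df test when style explained 2.2%, 3.8%, 5.9%, 8.3% and 13.8% of intercept variance. Its 6-df test stayed at about 6%.

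**Follow-up tests under item 17.** Take trials where style alone made the omnibus test significant, at r = 0.2, 0.3 and 0.4. At least one of the three gabapentin interactions is falsely significant in 22%, 15% and 15% (intercept and slope tested jointly), or 33%, 25% and 24% (tested separately). For the joint version the unconditional rates are about 0.22 × 0.55 = 12%, 0.15 × 0.94 = 14% and 0.15 × 1.00 = 15%.

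**Power of the alternatives** (2,000 trials each).

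| True effect on slope | 14 df | 8 df | 6 df |
|---|---|---|---|
| Uniform gabapentin 0.3 SD | 31% | 38% | about 6% |
| Uniform gabapentin 0.4 SD | 54% | 64% | about 6% |
| Uniform gabapentin 0.5 SD | 75% | 84% | about 6% |
| Three-way 0.15 SD | 29% | 36% | 40% |

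**The case against.** The best defence is that the formal hypotheses in item 8 are written as the likelihood ratio between these two models, so the test matches the formula. Item 17 then tests every term, including the three-way interaction, so a reader of the planned output could see whether style alone drove the result. With style effects only, the chance that the omnibus test passes and the three-way term is also significant (intercept and slope jointly) is about 3–6% at r = 0.2 to 0.4. Item 14 also foresees the gabapentin comparison with and without interactions.

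This softens the problem without curing it. The formula conflicts with the verbal hypotheses beside it, and neither item 14 nor item 17 governs the sentence that declares support. The false-positive rates for the follow-up terms are largely ordinary multiplicity, which the SAP openly leaves unadjusted. They show that item 17 is no safeguard and are not a second fault of the null model.

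Four further points stand:

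- Item 12 is only supporting evidence. It still refers to pupil responses to painful stimuli, which SAP 2.1 replaced in the primary analysis.
- A re-specified test would have no power basis stated in item 11.
- The sizes rest on assumed values, and at r = 0.1 the excess is modest.
- A contrast changed after the result was known would be post hoc.

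**Conclusion.** The concern holds. The interpretation rule in item 27a/27b is not supported by the test it is attached to, and it contradicts the verbal hypotheses in item 8. This follows from the model structure alone. The size depends on an assumed style–intercept correlation, assumed variances and complete diaries. Under those assumptions a style effect with no gabapentin effect gives a significant primary result in about 13–16% of trials at r = 0.1, about half at r = 0.2, and 84% or more from r = 0.3. A pupil effect, a style × pupil effect or a uniform gabapentin effect would be misread in the same way. Because this is the only confirmatory inference, it must be fixed.

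**What to change.** Replace the support sentence in item 27a/27b with one saying that a significant 14-df result means at least one of the added predictors or interactions improves fit. This is needed in any case.

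Put cognitive style, resting pupil diameter and style × pupil, each on intercept and slope, in the null model, so that the primary test covers only terms containing treatment. Choose one version and state it:

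- **8 df (treatment plus its three interactions).** This keeps gabapentin's overall effect, which belongs to the objective in item 8. A claim of interaction should then also require the 6-df test to reject.
- **6 df (interactions only, with treatment also in the null model).** This matches the verbal hypotheses and item 12, but has almost no power for a uniform gabapentin benefit.

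State the degrees of freedom for the other trajectory forms (8 becomes 12 or 16; 6 becomes 9 or 12). Keep the 14-df comparison as a secondary prognostic analysis, give a power statement for the chosen contrast, and reconcile items 8, 11, 12, 17 and 27a/27b.

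The cost is a text correction and one re-fit on the same data. The primary p-value loses the style and pupil contribution and will probably be less favourable. On timing, item 14 says that difficulties with the psychologic construct and pupil parameters "prevented completion of the primary analysis until Mar, 2023", while the latest revision is dated April 26, 2023. If the primary result was known when the contrast is changed, the new test must be dated and labelled post hoc.

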This will be presented in CONSORT diagram format rather than as a table, with numbers and reasons for withdrawal and/or exclusion from analysis given at each stage

24c. *Reasons for withdrawal/lost to follow up data*

The numbers (with reasons, if available) of losses to follow-up (drop-outs and withdrawals) over the course of the trial will be summarized by treatment arm.

25a. *List of baseline characteristics to be summarized*

Patients will be described with respect to age, sex, race, ethnicity, medications, number of painful conditions excepting the hip and their locations, cognitive – optimism cognitive construct generated from questionnaires, baseline pain from the daily diaries prior to surgery, and surgical approach (anterior vs posterior).

25b. *How baseline characteristics will be described*

Categorical data will be summarized by numbers and percentages. Continuous data will be summarized by mean, SD and range if data are normal and median, IQR and range if data are skewed. Minimum and maximum values will also be presented for continuous data. Tests of statistical significance will not be undertaken for baseline characteristics; rather the clinical importance of any imbalance will be noted.

Section 6: Analysis

26. *Outcomes and timings*

Primary outcome: Worst pain intensity measured using a 0 to 10 numerical rating scale on a daily diary. Measurements will be obtained each evening from day 0 (surgery) to day 56 after surgery. The pain measurements will be evaluated in a statistical model using an intercept (i.e., immediate pain after surgery) and slope (i.e., rate of change of pain during the observation period).

Secondary outcomes: Daily measurements such as physical activity, as measured via actigraphy, disability, as measured by daily diaries and weekly WHODAS 2.0 scores, and opioid self-administration, as measured by daily diaries will be collected from day 0 (surgery) to day 56 after surgery. Questionnaire and cognitive game data will be assessed at baseline and follow-up. Validated scoring systems from the individual items will be used to score each questionnaire or measure. These outcomes will not be used in the primary analysis.

27a. *Analysis methods to be used and*

27b. *Adjustments for covariates*

Primary analysis:

Overview

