1. Trajectories for daily activity, as measured via actigraphy, disability, as measured by daily diaries and weekly WHODAS 2.0 scores, and opioid self-administration, as measured by daily diaries, will be analyzed using a similar approach. As noted, other questionnaire and cognitive game scores will be described for the two groups but not analyzed or entered as covariates for the purpose of the primary analysis and publication. Changes in questionnaire data will be evaluated using the generalized linear model regressing follow-up score on baseline score and medication group assignment.

2. The contribution of pupil diameter change in response to acute preoperative pain testing to prediction of trajectory of change in postoperative pain intensity rating will be assessed. This will be performed in the same manner as the primary analysis. In addition, a 4 way-interaction test using the same approach as in the primary analysis will be used by included both pupil diameter at rest and its response to preoperative acute pain stimuli.

3. Development and internally validation a predictive model for recovery from pain from the full battery of preoperative questionnaires and application of item response theory to create a much smaller set of questions with retained predictive value for subsequent testing as a practical tool.

4. Modeling recovery of function from the World Health Organization Disability Assessment Score 2.0 (WHODAS 2.0), Western Ontario and McMaster Universities Osteoarthritis Index (WOMAC) and daily activity level as assessed using actigraphy in order to assess their relationships and those between these functional measures and daily pain, including lead-lag and influence of days of physical therapy, during recovery from physical therapy after lower extremity major total joint arthroplasty.

5. Examining the influence of anesthetic technique (general anesthesia, regional anesthesia via single injection regional anesthesia with sustained catheter infusion) on perioperative acute pain and pain and functional recovery over the subsequent two months.

6. Exploring biomarkers for stress and noradrenergic functioning by exploring the relationship between preoperative patient characteristics, including psychophysical responses to pain processing and CSF concentrations of norepinephrine and markers associated with stress.

27c. Methods to be used for assumptions to be checked for statistical methods for primary and secondary analyses

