The assumptions underlying parametric modeling will be evaluated using regression diagnostic procedures and histograms of residuals.

27d. Alternative methods to be used if distributional assumptions do not hold for primary and secondary analyses

If necessary, the primary outcome distribution will be log transformed to satisfy assumptions. For secondary outcomes, the generalized linear model allows the specification of an array of distributions (e.g., normal, binomial, gamma) with corresponding link functions (e.g., log).

27e. Planned sensitivity analyses

Four sensitivity analyses will be performed to evaluate the robustness of the trajectory analysis to the primary and secondary analyses. These are to include multiple imputation for missing data, to include baseline measures of primary and secondary outcomes as predictors in the trajectory models, to include monthly through 6 months and the 12-month daily diary data and to include patient race and surgeon as other causes of variability in trajectory in the primary analysis.

27f. Planned subgroup analyses

No subgroup analyses are planned.

28. Missing data – reporting and assumptions/statistical methods to handle missing data

Multiple imputation will be used to account for embedded missing data in daily diary entries. The autocorrelation of each time-series for each individual along with baseline predictors will be used in conjunction with the MICE algorithm to estimate $m = 20$ imputations. These imputations will then be re-analyzed using the primary model with Rubin's rules used to pool the estimates of model parameters.

29. *Details of any additional statistical analyses required e.g., complier-average causal effect analysis.*

None

30. *Harms*

The number (and percentage) of patients experiencing each AE/SAE will be presented for each treatment arm categorized by severity. For each patient, only the maximum severity experienced of each type of AE will be displayed. The number (and percentage) of occurrences of each AE/SAE will also be presented for each treatment arm. No formal statistical testing will be undertaken

31. *Statistical Software*

The analysis will be carried out using R version 4.1.2

32. *References*

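### The exploratory questionnaire comparison regresses one unnamed follow-up score on baseline and arm only, although two follow-up scores, study site and surgery type are available at almost no cost

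*SAP*

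**What the plan says.** - **Model.** Section 27a/27b, exploratory secondary analyses, item 1: "Changes in questionnaire data will be evaluated using the generalized linear model regressing follow-up score on baseline score and medication group assignment". The outcome is one score, its visit is not named, and baseline score and arm are the only predictors.
- **Timing.** Section 26 says only: "Questionnaire and cognitive game data will be assessed at baseline and follow-up". Table 1 (Section 14) marks questionnaires at Visit 1 (baseline), Visit 2 (week 8) and Visit 3 (week 26). Each patient can therefore give two scores after surgery.
- **Primary model adjusters.** The operative characteristics in Section 27a/27b: "study site, and surgery type (hip or knee arthroplasty) will be entered into the model". Age and sex are entered as well.
- **Stratification.** Section 10: "The randomization will be stratified based on study recruitment site, concurrent use of a serotonin-norepinephrine reuptake inhibitor, and chronic low- or high-dose opioid therapy". Site is thus both a stratum and a primary-model covariate.
- **Missing data.** Section 28: "Multiple imputation will be used to account for embedded missing data in daily diary entries", followed by "These imputations will then be re-analyzed using the primary model with Rubin's rules used to pool the estimates of model parameters". The sensitivity analyses in Section 27e concern the trajectory models. Neither section mentions questionnaire scores.
- **Neighbouring sentence.** Just before the regression, item 1 says that other questionnaire and cognitive game scores will be described by group, without analysis, as far as the primary analysis and publication are concerned. How this fits with the regression is not explained.

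**The concern.** This regression is the only stated treatment comparison for the week-8 and week-26 questionnaires, and it uses less than the trial collects.

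1. **Visit and missing scores.** The text does not say whether week 8, week 26 or both are analysed. With a separate regression per visit, a patient with a week-8 score but no week-26 score is absent from the week-26 comparison, and nothing elsewhere in the SAP brings that patient back. The week-8 score, which carries information about the missing one, goes unused.
2. **Adjusters.** Site and surgery type are known before surgery and already enter the primary model. Leaving them out here, with no reason given, leaves in residual variance that could be removed.

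At stake are some precision and, under particular dropout patterns, a biased arm difference at the visit with missing scores.

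**Working it through.** The SAP gives no sample-size figure for this analysis. Its 250 patients and power above 90% belong to the primary likelihood ratio test, and the inputs of that simulation are not given, so there is nothing to reproduce.

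**Inputs from the SAP:** 250 patients, 1:1 allocation (125 per arm), two-sided 5%, two follow-up visits.
**Assumed, because the SAP gives no value:** missingness, correlations, effect size, and variance explained by the adjusters.

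**1. Patients left out of the week-26 comparison with week 8 in hand.** If week 8 is complete and a fraction m misses week 26, this is 250 × m: 25, 50 and 75 for m = 10, 20 and 30%. If the two visits are missed independently it is 250 × m × (1 − m): about 22, 40 and 52.

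**2. Precision gained by modelling both visits.** With week 8 complete and residual correlation ρ between visits, the week-26 SE of the joint model relative to the per-visit model is √(1 − mρ²).

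| ρ | m = 10% | m = 20% | m = 30% |
|---|---|---|---|
| 0.3 | 0.995 | 0.991 | 0.986 |
| 0.5 | 0.987 | 0.975 | 0.962 |
| 0.7 | 0.975 | 0.950 | 0.924 |

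The SE falls by about 0.5 to 8%.

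**3. Precision gained from site and surgery type.** If they explain a share R² of residual variance, the SE is multiplied by √(1 − R²). The power column is for an arm difference of 0.30 SD, baseline correlation 0.5 and no missing scores. Without the adjusters the SE is √0.75 × √(2/125) = 0.110 and power is 78.2%.

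| R² | SE ratio | Power |
|---|---|---|
| 1% | 0.995 | 78.6% |
| 2% | 0.990 | 79.0% |
| 5% | 0.975 | 80.2% |
| 10% | 0.949 | 82.3% |

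A larger gain needs a large hip-knee difference that remains after baseline adjustment. In simulation the SE went from 0.137 to 0.125 at a difference of 0.8 SD ((0.137/0.125)² = 1.20, worth 20% more patients), from 0.126 to 0.122 at 0.5 SD, and hardly moved at 0.3 SD.

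**4. Bias from missed week-26 visits.** Simulation with 250 patients, true difference -0.30 SD at both visits (higher score = worse), baseline correlation 0.4, week 8 to week 26 correlation 0.65 and about 17% missing at week 26. Missingness depends on the week-8 score through an odds ratio (OR) per SD.

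| Dropout mechanism | Per-visit model | Joint likelihood model |
|---|---|---|
| Unrelated to week-8 score | -0.30 | -0.30 |
| Same in both arms, OR 1.65 or 2.7 | -0.29 | -0.30 |
| Worse placebo patients only, OR 1.65 | -0.26 | -0.30 |
| Worse placebo patients only, OR 2.7 | -0.22 | -0.30 |
| Better placebo and worse gabapentin patients, OR 1.65 | -0.38 | -0.30 |
| Better placebo and worse gabapentin patients, OR 2.7 | -0.45 | -0.30 |

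The bias can go either way. The joint model removes it here because missingness depends only on an observed score. It would not do so if missingness depended on the unseen week-26 value itself.

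**The case against.** **The analysis is low stakes.** It is listed as exploratory, Section 26 keeps these outcomes out of the primary analysis, and weekly WHODAS disability already goes through the trajectory approach. This stands, and it sets the priority.

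**The method is valid as written.** Baseline-adjusted regression at each visit is standard. In a randomised linear comparison, omitting site and surgery type costs precision and does not bias the estimate. This stands for the identity link. Section 27d also allows other links, under which adding or omitting a prognostic covariate can change the quantity estimated.

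**Strong arm-specific dropout is speculative.** The SAP gives no dropout figures, and Table 1 ends study drug three weeks after surgery, so loss between weeks 8 and 26 begins at least five weeks later. This makes a strong arm-specific mechanism less natural, though not impossible.

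A reader might infer three stronger claims that the SAP does not support:

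- *The plan discards patients.* It never says so. Exclusion is the default behaviour of a one-outcome regression with no missing-data method, it affects only the missed visit, and the patient still counts at the other.
- *The test runs at 11 to 12% instead of 5%.* That would follow if both visits were stacked as independent rows: P(|Z| > 1.96/√(1 + ρ)) = 0.110 at ρ = 0.5 and 0.119 at ρ = 0.58. The SAP proposes no stacking; it speaks of a score in the singular.
- *The comparison is biased.* That requires dropout related to the other score differently by arm, for which the SAP offers no evidence either way.

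**Conclusion.** The point holds as a cheap improvement to an exploratory analysis. The regression leaves the visit unnamed, omits two adjusters that the SAP uses in its primary model, and has no method for missing scores although a second follow-up score is often at hand.

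Under the assumed inputs, the adjusters lower the SE by about 0.5 to 5%, and by more only with a strong hip-knee difference after baseline adjustment. Joint modelling lowers the week-26 SE by about 0.5 to 8%. Bias is about 0.01 SD when dropout acts alike in both arms. In the arm-specific mechanisms tried, the estimate ranged from -0.22 to -0.45 against -0.30. These figures show what could happen and do not estimate what happened in this trial. Low priority: worth considering, and no obstacle to the primary analysis.

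**What to change.** Replace the sentence with:

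*Questionnaire scores at weeks 8 and 26 will be analysed together in a likelihood-based repeated-measures mixed model with baseline score, visit, arm, arm × visit, study site and surgery type (hip/knee), and an unstructured within-patient covariance. The arm difference will be reported at each visit. Non-normal scores will use a generalized linear mixed model, or multiple imputation using the other visit's score followed by a marginal model.*

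Unweighted GEE should not be the fallback, since it generally needs scores to be missing completely at random and so need not remove the dropout bias shown above. For a non-identity link, state whether the effect reported is conditional or marginal.

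Also state how this analysis relates to the preceding sentence, under which other questionnaire scores are only described for the primary analysis and publication.

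Cost: SAP wording and a few lines of code, with no new data. The SAP already uses mixed-effects models for its daily outcomes. The downside is a slightly longer model.
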